Households for observation of CHW counseling to caregivers will be consecutively recruited from the enrolled caregiver cohort in the MRV-CCD intervention group. As caregivers are enrolled, their household location will coincide with a particular CHWs' catchment area and they will be matched to their respective CHW. With an expected 607 caregivers enrolled in the MRV-CCD group and even distribution by age group, we would expect about 150 to have children less than 6 months, 150 with children 6-11 months, and 300 with children 12-23 months. Also assuming even distribution of

enrolled caregivers by CHW catchment areas and by child age group, we would expect each CHW (about 120) to have about 5 caregiver-cohort enrolled households. The study coordinator will select caregivers for CHW observations largely consecutively, but will also purposely select caregivers of children if different age groups.

Data Collection: CHW Cohort

CHW's will be asked to complete baseline and endline structured interviews, and agree to being observed, at baseline and endline, during two group education sessions at the facility and two home visit counseling sessions with caregivers.

Pre-post questionnaire: At baseline the enrolment form will be used to collect information, using a structured tablet-based interview, on CHW characteristics (demographics, history of CHW work), training, ECD knowledge and attitudes. This form will be re-administered at endline, including a module on CHW use of, and attitudes toward the ECD videos.

Observation checklists: Two separate observation checklists will be completed by the RA, one for clinic health education session and another for the home session. These checklists will document (a) background information on the environment and participants (home/clinic, caregiver relation to the child, child age [home], or number of clients in the education session and topics discussed [clinic]); and (b) score a series of items describing what the CHW did on a two or three-point scale (done/not done or done, partly done, not done). These scored items are either the "soft skills" of mentoring, such as "actively listens to the caregiver with minimal interruption" or practical behaviors that help to build caregiver skills in early stimulation such as "asks how the caregiver gets the child to smile." The checklists at endline will assess specific aspects of video use, which will not be applicable at baseline.

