Clinic observations: As described above, the RA will liaise with the nurse in-charge to know the CHW duty roster in order to schedule clinic observation visits. CHWs should not know in advance which day they will be observed, though it will be impossible for the CHW not to be aware of the observer once the session begins. Prior to the session starting, the RA will introduce him/herself to the caregivers attending the CHW's counseling session and explain his/her purpose for being there. We are requesting a waiver of informed consent for the observations as described below. Any caregiver who prefers not to be part of the session for any reason will be excused. The clinic sessions will last from 10-60 minutes.

Home observations: Each enrolled CHW will be observed at two home visits with two different caregivers. The RA will focus on observing the CHW's behaviors in mentoring and providing feedback to caregivers on ECD and early stimulation (CCD). The observing RA will explain to the CHW that s/he should do what they normally do to assess, support, educate and mentor caregivers during a home visit. While the CHW may discuss health issues beyond CCD (immunization, postnatal care, medical referrals for illness, etc.), the data collection tool completed by the RA will be focused on observing and rating of behaviors/practices and interactions related to CCD only.

Home visit sessions will also be audio/video recorded using lapel cameras worn by the CHW and the caregiver. Collecting video observations is a standard observational tool that allows for rigorous coding of counselor behaviors. Lapel video cameras are unobtrusive and can be worn by the CHW and caregiver in a manner that captures both perspectives. Thus, two separate videos of each

session will be viewed by independent RAs who will complete the checklist, in addition to the RA who will be present at the session and scoring the observation checklist in real time.

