Only caregivers who have consented to participate in the study cohort will be visited for CHW observations. On arrival at the caregiver's home, the RA will first remind the participant about the study and reconfirm caregiver consent to being observed by the RA and video-recorded during the session before the CHW proceeds with the home visit observation. Caregivers will be free to decide not to be observed, or to allow observation without video recording, without penalty; the CHW counseling session will proceed with or without these evaluation components. The home sessions will last about 10-60 minutes.

Outcome and Measures: CHW Cohort

Outcomes characterizing CHW capacity and the quality of CHW-caregiver interactions, and how CHW capacity and mentoring skills may change between baseline and endline after introduction of ECD videos, are grouped into four main categories:

1. CHW knowledge: of ECD and early stimulation
2. Compliance with message delivery: How well does the CHW demonstrate clear communication of ECD messages?
3. Responsiveness and listening skills: Does the CHW demonstrate good listening and communication skills, establishing good rapport and showing empathy?
4. Acceptability of videos: Whether CHW report video job aid to be useful, user friendly and acceptable and whether any challenges with use were observed or reported.

Given their potential to modify CHW capacity to deliver the intervention, the following characteristics and standard assessments will also be completed with CHW.

IQ - Ravens Standard Progressive Matrix (Ravens): Refer to above description.

Mental health, depression/anxiety (PHQ-9, GAD-7): Refer to above description.

CHW reported activities: The intensity and frequency of CHW responsibilities (e.g. number of households visited, frequency of visits) will be assessed in the pre/post structured interviews, as well as CHW training and duration of working as a CHW.

Media listenership: Questions from the caregiver listenership will be included in the CHW baseline/endline questionnaires, assessing exposure to radio communication, and recall of health education messages (including ECD-related) with respect to content, and source.

Scoring observations of CHW sessions

Video observations will be coded and scored by trained staff using a standardized checklist, and a sample of 20% of all videos will be double coded by another trained member of the study team to ensure reliability of coding.

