Observation checklists for each CHW, by type of observation (clinic, home) and timing of observation (baseline, endline), will be averaged across all measures. Thus, a CHW's baseline or endline home score will be the average score of the in-person observation checklist scores (2 data points) and the video scores from two home visits (2 data points). A CHW's clinic score at baseline or endline will be

the average of two data points, based upon the in-person observation checklist scores at two clinic sessions. Each checklist score will impute missing values as the mean score for other values in that section, and an observation with more than 20% missing values will be considered invalid (and should be re-done).

Process Evaluation: MRV-CCD Group

The primary purpose of the process evaluation is to establish the fidelity of CHWs to the full Malezi II intervention package, specifically monitoring CHW practices and use of the short videos throughout the intervention period. The process evaluation component will also systematically collect routine program monitoring data from the MRV-CCD index facilities and CHWs with respect to developmental referrals made, number of group session held, and number of CHW home visits reported.

During the 9-month exposure period, research associates will aim to conduct CHW observation checklists (as designed for the baseline/endline data collection) on each MRV-CCD group CHW at least once/quarter for clinic sessions and twice/quarter for home sessions. This translates to about 246 home and 123 clinic checklists completed per quarter (total 369), or about 185/RA/quarter, or roughly 3 per day.

Focus group discussions

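### Half of the CHW home score and all of the clinic score come from raters who know the round, and masked or mixed-order video coding is not required, so rater shifts enter the uncontrolled Objective 3 change

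*Protocol*

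**What the plan says.** Under Scoring observations of CHW sessions, the protocol sets the home score at each round as "the average score of the in-person observation checklist scores (2 data points) and the video scores from two home visits" (two data points from each source), and the clinic score as "the average of two data points, based upon the in-person observation checklist scores at two clinic sessions". No recording of clinic sessions is described.

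Under Data Collection: CHW Cohort (home observations), recordings go to independent RAs, "in addition to the RA who will be present at the session and scoring the observation checklist in real time". Under the same heading, on the observation checklists: "The checklists at endline will assess specific aspects of video use, which will not be applicable at baseline".

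On coding, the scoring section says "Video observations will be coded and scored by trained staff using a standardized checklist" and adds that a 20% sample is coded a second time for reliability. It gives neither the time nor the order of coding, and does not say whether coders know the round.

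Between the rounds, under Process Evaluation: MRV-CCD Group, "research associates will aim to conduct CHW observation checklists (as designed for the baseline/endline data collection") at least once per quarter in clinic and twice per quarter at home for each CHW. The Data Analysis section treats Objective 3 as a baseline-to-endline comparison within the CHW cohort, which comes from the MRV-CCD group only.

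**The concern.** Many checklist items call for judgment on a two- or three-point scale, for example whether the CHW listens actively. An RA who sits in the home at endline knows that training and videos have been introduced, and may have watched the same CHW several times during the exposure period. Expectation and familiarity can both move the score while the behavior stays the same.

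With a comparison group rated in the same way, such a shift would tend to cancel. Here there is none, so it is added to the estimated change. The independent scoring of recordings offers protection, but the protocol averages it equally with the live score. That protection is itself only as good as the coding order: if baseline recordings are coded in one period and endline recordings about a year later, coders who drift together would still agree with each other, and the double coding would not show it.

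**Working it through.** **1. The plan's own figure.** Table 5 uses McNemar's test at the 5% level (two-sided assumed), with 50% rising to 65%, correlation 0.4 and 80% power.
- Both positive: p11 = 0.5 × 0.65 + 0.4 × √(0.5 × 0.5 × 0.65 × 0.35) = 0.4204.
- Discordant share: pd = (0.5 − 0.4204) + (0.65 − 0.4204) = 0.3092; d = 0.15.
- n = [1.96 × √0.3092 + 0.8416 × √(0.3092 − 0.0225)]² / 0.15² = 105.5, so 106.
- Inflated: 106 × 1.1 / 0.95 = 122.7, so 123. Both figures match Table 5. The sample size is not at issue, because a larger sample does not reduce a rating bias.

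**2. Weight of the in-person score.**
- Home: 2 of 4 data points, w = 0.5.
- Clinic: 2 of 2 data points, w = 1.

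**3. What enters the change.** Let b be the shift in in-person scores between rounds for identical behavior, and v the drift in video scores. The spurious change is w·b + (1 − w)·v. For the home score this is 0.5b + 0.5v; for the clinic score it is b. Neither b nor v is given in the protocol, and either could be negative.

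**4. Illustration.** Assume b = 3 to 8 points. The planned change is 15-20 points (Sample Size Calculations, Objective 3).

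| Case | Spurious points | Share of 15 | Share of 20 |
|---|---|---|---|
| Home, v = 0 | 1.5 to 4 | 10-27% | 7.5-20% |
| Home, v = b | 3 to 8 | 20-53% | 15-40% |
| Clinic | 3 to 8 | 20-53% | 15-40% |

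**5. Effect on the test.** In the McNemar model of step 1 with n = 106, no true change and v = 0, an assumed b of 5 points moves the home score by 2.5 points and raises the rejection rate from 5% to 7.5%. The clinic score moves by the full 5 points, with a rate of 15%. At b = 10 the rates are 15% and 46%. These depend on treating the score as a proportion, as Table 5 does.

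**6. Two things that change the weight.**
- The home-observation text speaks of two separate videos per session. If that meant four video scores, the in-person share would be 2/6 = 1/3, and the same b with v = 0 would add 1.0 to 2.7 points. The scoring rule counts two.
- Caregivers may refuse recording. If the remaining points are simply averaged, one refusal in a round raises the share to 2/3 and two raise it to 100%. If refusal differs by round, the rating mode changes with time.

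**7. Familiarity.** The process evaluation plans at least 3 observations per CHW per quarter, so about 9 over three quarters. Its workload of 369 checklists per quarter at about 185 per RA implies 369 / 185 ≈ 2 RAs. The protocol does not separate them from the baseline and endline raters.

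**The case against.** The strongest defense is that the protocol contradicts nothing. Averaging live and recorded ratings is a legitimate choice: four data points are less noisy than two, and a person in the room may see what a lapel camera misses. Coding order is often set in a coding procedure or analysis plan, and the SAP is not at hand. This stands in part. Silence on order is not the fault in itself; the point rests on the equal weighting that the protocol does fix, and on what that weighting does in an uncontrolled comparison.

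Three stronger readings are tempting and should be resisted.
- A reader might infer that the recordings will be coded round by round. The protocol does not say so; it only fails to require otherwise.
- A reader might infer that averaging throws away the value of the recordings. It dilutes it: half of the home score still comes from independent coders.
- A reader might infer that everything under Objective 3 is exposed. CHW knowledge is a listed outcome collected by structured interview, and it does not depend on an observer's rating of a session.

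The defense is also right that a careless remedy would cause harm. An observation with more than 20% missing values should be repeated, and a baseline visit cannot be repeated after endline. Filling refused recordings with in-person scores would mix two rating modes in one score.

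**Conclusion.** The point holds in this form: the protocol fixes a 50% unmasked share in the home score and a 100% unmasked share in the clinic score, does not require masked or mixed-order coding of the recordings, and has no comparison group to absorb a change in rating. The clinic score is the more exposed of the two.

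The mechanism and the weights come from the document; the size does not. The 1.5-4 points for the home score rest on an assumed in-person shift of 3-8 points with no video drift, and should be read as an illustration of scale. On that assumption the home change would be distorted by a noticeable fraction of its target, without accounting for all of it. This is worth correcting because the recordings are already planned and the remedy needs no new data.

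**What to change.** 1. **Coding.** Check each recording for technical usability at the time of the visit, so that the rule on repeating invalid observations can still be applied. Do the scored coding of baseline and endline recordings together after endline, in random mixed order, without dates or visit labels. Use coders who did not attend those sessions and, where staffing allows, did not observe those CHWs in the process evaluation. Score the items common to both rounds first, and the video-use items in a second pass.
2. **Reporting.** Report the recording-based and in-person home scores, and their changes, separately and not only as an average. Base the main Objective 3 home conclusion on the recording-based change in CHWs recorded at both rounds. Do not substitute in-person scores for refused recordings within that score, and report refusals by round.
3. **Clinic score.** State that it rests wholly on unmasked in-person rating, and interpret its change with that limitation.

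The cost is mainly scheduling and file naming, with the same recordings and largely the same staff. Coding finishes later. The recording-based score has two data points per CHW and round where the average has four, and restricting it to CHWs recorded at both rounds reduces the number analyzed by an amount that depends on refusals, for which the protocol gives no estimate. Masking stays incomplete when a job-aid video is in view or the child's age gives a cue, but mixed order still removes drift between coding rounds. Moving the main conclusion away from the average trades some precision for less bias; reporting both scores lets readers see that trade.

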The Malezi I intervention was found to be feasible and acceptable as an integrated intervention within routine MNCH/PMTCT services. The internal Malezi I program evaluation, using a pre/post design, found substantial increases in caregiver knowledge and practices as reported through exit and household-based interviews. Knowledge among facility-based health providers and CHWs also increased significantly, and health providers reported increased access to ECD resources.

Given the existing and emerging evidence on potential strategies to better engage communities in supporting health promotion interventions, the Malezi II grant will expand Malezi I coverage of CCD program implementation to nearly double the number of facilities supported, and introduce additional components, specifically, a mass media campaign and video job aids. The addition of video job aids aims to further support and improve CHW education and counseling skills, and the addition of radio messaging aims to promote perceptions and knowledge of ECD, and possibly responsive caregiving behaviors, more broadly at the community level.

The Malezi II program, additional multi-media components, and theory of change model informing the evaluation

The Malezi II grant supports a continuation and expansion of the Malezi I CCD program described earlier, plus two additional interventions related to multi-media communications aimed at improving ECD perceptions, knowledge and responsive caregiver behaviors. These two approaches include a mass media communication strategy using radio messaging and the introduction of short video job aids, along with capacity building training for community health workers in the use of those job aids. This study is designed to evaluate the comparative effectiveness of the two interventions with respect to ECD perceptions, knowledge and responsive caregiving outcomes. In addition, by analyzing differences between baseline and endline within each study group (pre/post design), we will describe the effectiveness of radio messaging alone compared to no radio messaging, and the effectiveness of a fully integrated ECD intervention, including radio messaging, short video job aids and Malezi CCD program support compared to CCD program support without radio and short video support.

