- To what extent does the Malezi II radio messaging reach caregivers of young children?
- To what extent are caregiver ECD perceptions, knowledge and reported parenting practices changed after introduction of Malezi II radio messaging to their communities?
- Is there a relationship between reported listenership and/or message recall (dose) and caregiver ECD perceptions, knowledge and reported parenting practices?
- To what extent does exposure to the Malezi II full intervention (MRV-CCD: radio messaging, video job aids, continued CCD program support) improve caregiver knowledge and parenting practices?
- Does exposure to the Malezi II full intervention (MRV-CCD) improve caregiver knowledge and parenting practices significantly more than exposure to radio messaging alone (MR)?
- To what extent do the CHWs adhere to the Malezi II training with regard to use of the video job aids, delivery of complete and accurate ECD messages, and general quality of counseling support?
- Do the Malezi II video job aids improve the quality of CHW ECD counseling support given to caregivers in clinic and home settings?

METHODOLOGY

This study is a two-arm quasi-experimental pre-post evaluation design, comparing two interventions to establish their relative impact on caregiver knowledge and behaviors/practices among a cohort of caregivers of children 0-24 months at enrolment (baseline) and under three years after a 9-month

intervention exposure period (endline). In addition, the quality of counseling support to caregivers, at health facilities and through home visits, will be assessed at baseline and endline in a cohort of CHWs recruited from the MRV-CCD full intervention group. Figure 2a provides an overview of the research design for objectives 1 and 2. Figure 2b provides an overview of the research design for objective 3.

[figure not shown]

Figure 2a. Research design overview – community component

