The radio messaging in both intervention groups, and the short videos in the second intervention group (only) will be introduced after the baseline assessment of the caregiver cohort. The exposure period for the two interventions, as described in Table 2, will be for nine months, followed by the endline assessment of caregivers.

Table 2. Description of intervention packages in two study arms

Intervention group	Description and expected exposure (dose)
Malezi II minimum package Radio (MR)	Radio messaging spots Dose: Up to 35-40 different messages, 3 stations aired on (2 regional, 1 national), about 10 times per day; 7 days per week airing frequency; 9 months duration of exposure 
▪ Caregiver exposure to radio messaging during 9-month period: currently unknown, but estimated at 50% of caregivers hearing about 7 messages/week.
Malezi II full package Radio, Video Job Aids, CCD program (MRV-CCD)	Radio messaging spots 
▪ Same as MR group

MRV-CCD	
Short video ECD job aids (with training)
 
Five short ECD mobile films (videos) of 3-5 minutes each will feature a mixture of real-life testimonies and scripted interactions between health workers and caregivers, and demonstrations of caregivers stimulating their young child. Each video will show a range of age-appropriate ECD practices that encourage child development (play; communication; positive caregiver-child interaction; safe/stimulating environment; positive discipline), illustrating skills and providing knowledge. All videos will have some cross-cutting content, emphasizing the general benefits of ECD activities during the early years, and one video will be devoted exclusively to cross-cutting parental guidance on developmental milestones and benefits of applying ECD practices. Four videos will target specific age groups (0-5, 6-11, 12-23, >=24 months).
 
Caregiver exposure to group counseling at clinic is estimated to be 2-4 sessions in a 9-month period
 
Caregiver exposure to individual counseling at home is estimated to be 3-6 sessions in a 9-month period

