Descriptive statistics (range, median, mean, percent) will be used to review the data overall and describe participant background characteristics, radio listenership patterns and parenting perceptions, knowledge and practices, identifying any baseline differences in population by study group. Confidence intervals (CI) will be calculated around summary measures and statistical tests of significance (non-parametric) will be applied where appropriate to compare the distribution of characteristics or outcomes across study groups. The effects of radio exposure only (objective 1) will be described by comparing study outcomes at baseline and endline within the MR study group only. Within study group differences in study outcomes will be described comparing distributions of responses to key outcome variables at baseline and endline using statistical testing appropriate for paired groups such as the paired t-test, Wilcoxon or McNemar's tests. Regression modelling may be used to estimate the intervention effect while controlling for covariates.

The additional effects of the combined exposure to radio, short videos and Malezi CCD (MRV-CCD; objective 2), as compared to the radio only effect, will be described using a differences in differences (DID) analysis. The treatment effect can be found by obtaining the proportion of caregivers with the outcome in the MRV-CCD and MR groups at both time periods. The difference in outcomes between study groups at both time periods may be charted to visualize the DID as shown in Figure 4, whereby the DID is what remains after subtracting the baseline differences between the two groups from the endline differences (30-5% = 25%). This will give an estimate of the extent of the improvement by the Malezi II full intervention. We will use regression modelling to estimate the intervention effect while controlling for covariates. We will use the following general form model:

$$Y = \beta_0 + \beta_1[\text{Intervention}] + \beta_2[\text{Time}] + \beta_3[\text{Intervention} \cdot \text{Time}] + \beta_4[\text{Covariates}] + \varepsilon$$

The interaction term coefficient β_3 will also estimate the extent of the DiD.

[figure not shown]

Figure 4. Differences in differences analysis graphic

Objective 3: Community Health Worker Cohort

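### Objective 1 reads the before-after change in the radio arm as radio versus no radio, although every index child is about a year older at endline

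*Protocol*

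**What the plan says.** Under Data Analysis, Objectives 1 and 2: Caregiver Cohort, the protocol states that the effect of radio "will be described by comparing study outcomes at baseline and endline within the MR study group only", using paired tests. Adjustment is permitted but not required: "Regression modelling may be used to estimate the intervention effect while controlling for covariates". For objective 2 the same section commits to regression.

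The section on the Malezi II program and theory of change gives the within-arm change a comparative reading: "we will describe the effectiveness of radio messaging alone compared to no radio messaging". The second item under Research Questions is more cautious and asks how far outcomes are "changed after introduction of Malezi II radio messaging to their communities".

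On timing, Intervention Description says the radio messages "will be introduced after the baseline assessment of the caregiver cohort". The same caregivers and index children are surveyed twice, with children aged 0–24 months at enrolment and under three years at endline.

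On child age, Table 2 says of the videos: "Each video will show a range of age-appropriate ECD practices that encourage child development". Four of the five videos are each aimed at one age band: 0–5, 6–11, 12–23, and 24 months or more. Outcomes and Measures: Caregiver Cohort names caregiver cognition, parenting stress and depression as possible confounders or covariates. Child age is not among them.

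**The concern.** Radio is to reach all of Tabora, so there is no concurrent group without it. In the planned comparison the no-radio state is the same households about a year before, when every index child was about a year younger. Objective 1 covers reported parenting practices as well as perceptions and knowledge. How often a caregiver reads to, plays with, disciplines or keeps toys for a child can plausibly depend on the child's age, and the protocol itself builds its video content around age bands. A paired change in such a practice is then the sum of ageing, secular trend and radio, and the paired test cannot separate them.

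The objective is sized for a change of only 5 points, so a modest age gradient could produce or hide the whole planned effect. The results are meant to inform decision makers on radio's effectiveness.

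**Working it through.** **Inputs.** From Sample Size Calculations, Objective 1 and Table 3: 10% to 15%, n = 420 before inflation, correlation 0.4, 5% significance, 15% loss, design effect 1.2, 593 enrolled. From Table 1: baseline survey 2–3 months, training 1 month, exposure 9 months, endline 2–3 months. From Sampling for Observed Sessions, for the full-intervention arm: "we would expect about 150 to have children less than 6 months, 150 with children 6-11 months, and 300 with children 12-23 months". Age eligibility is the same in the radio arm. From Sampling within Study Communities: about 250–300 enumeration areas (EAs).

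**1. Reproduce Table 3.** With p11 = p1·p2 + r·√(p1q1p2q2), p10 = p1 − p11, p01 = p2 − p11, s = p10 + p01 and d = p2 − p1:

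n = [(1.96·√s + 0.842·√(s − d²)) / d]²

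For 10% to 15%, p11 = 0.015 + 0.4 × 0.1071 = 0.0578, so s = 0.0422 + 0.0922 = 0.1343. Then n = [(0.7183 + 0.3055) / 0.05]² = 419.3, rounded up to 420. Inflated, 420 × 1.2 / 0.85 = 592.9, or 593. The other two rows also reproduce (419 and 411). The arithmetic of Table 3 is not in question.

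**2. Interval between surveys.** If endline visits follow the baseline order, the gap is about 9 + 2 = 11 months (training inside the baseline window) to 3 + 1 + 9 = 13 months.

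**3. Shift in child age.** The 150/150/300 split is 25/25/50/0% in the bands 0–5, 6–11, 12–23 and ≥24 months. Twelve months later it is 0/0/50/50%. At 11 months it is 0/4/50/46%, and at 13 months 0/0/46/54%. At a 12-month gap the share aged 12–23 months is the same at both surveys, so

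drift = 0.5 × (prevalence at 24–35 months − prevalence at 0–11 months).

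A 4-point difference gives 2 points of drift; a 10-point difference gives 5.

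**4. What drift does to the paired test.** Assume radio has no effect. The probability of significance is Φ[(d√n − 1.96√s) / √(s − d²)] plus the small opposite tail, with n = 420 and r = 0.4. For a 2-point drift from 10%, s = 0.1180, and (0.4099 − 0.6733) / 0.3429 = −0.768, which gives 22%.

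| Drift (points) | 10% baseline | 25% baseline |
|---|---|---|
| 1 | 9% | 7% |
| 2 | 22% | 14% |
| 3 | 42% | 25% |
| 4 | 63% | 39% |
| 5 | 80% | 55% |

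The nominal rate is 5%. Five points over 12 months is about 0.4 points per month of age. Downward drift matters too: a true 5-point gain with 2 points of downward drift appears as 3 points, and the chance of detecting it falls from 80% to 42%.

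**5. Precision of an age-adjusted estimate.** Simulation with 593 × 0.85 = 504 caregivers, 125 or 150 EAs in the radio arm (half of 250–300, an assumption), correlation about 0.4, design effect on the change about 1.2, a gap of 11.5 or 12.5 months, and a linear probability model with EA-clustered standard errors. For a true 5-point effect and no drift:

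| Model | Standard error | Power |
|---|---|---|
| Time only | 0.0174–0.0176 | 0.81–0.83 |
| Time + 6-month age bands | 0.028–0.030 | 0.38–0.42 |
| Time + linear age | 0.027–0.028 | 0.43–0.47 |

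With no radio effect and drift of 2 or 5 points under four shapes of age gradient, the banded model rejected in 4–6% of runs and the linear-age model in 4–9%. Bands are therefore the safer choice. The age overlap between surveys is (24 − gap)/24, or 46–54% for gaps of 13 to 11 months.

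**The case against.** The best counter-argument is that objective 1 does not rest on the paired change alone. The protocol expects about half of caregivers to hear the messages, measures listenership as dose, and asks whether dose relates to outcomes. Exposed and unexposed caregivers are compared at the same endline, so the cohort's ageing does not drive that contrast. This stands as far as it goes. But listeners select themselves, and the Data Analysis section gives the dose question no analysis; it defines the radio effect as the within-arm change.

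It can also be said that the sentence with the no-radio reading calls itself a pre/post design, and that covariate choice belongs in a statistical analysis plan. The covariate list also omits socioeconomic status and caregiver age, so the absence of child age is weak evidence that it would be left out. That is fair, and naming child age is a small part of the point. The comparative reading and the optional status of adjustment are nevertheless set in the protocol, and the weaker commitment falls on the analysis with no concurrent comparator.

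The size of the bias is unknown. Age-specific videos show that suitable practices change with age, not that an indicator's prevalence rises. This is correct: the rejection rates are conditional on an assumed drift. Lastly, aim 1 is about awareness, which is probably less affected, and the adjusted model is imprecise. Both points limit the scope and the remedy, but neither makes the no-radio reading sound for practices.

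**Conclusion.** The concern holds for the practice outcomes of objective 1. A significant paired change in the radio arm cannot be read as radio against no radio, because ageing of every index child by about a year is part of the same change. That the contrast is confounded follows from the design. How large the bias is does not: the documents give no age-specific prevalence, so the 9–80% range at a 10% baseline rests on assumed upward drifts of 1 to 5 points, and the true drift could be zero or negative. The age-shift calculation also assumes that the radio arm has the age split expected in the other arm and a gap near 12 months.

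The difference-in-differences for objective 2 is little affected if age mix and age gradient are similar in the two arms. This should be fixed; it does not call for a redesign.

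**What to change.** 1. In the section on the Malezi II program and theory of change, replace the claim of effectiveness against no radio with *change after radio introduction*, in line with Research Questions. This is the essential step.
2. In Data Analysis, for practice outcomes only, turn the optional regression into a planned one on time and child age at each interview in 6-month bands. Cluster standard errors at EA level, which also covers repeat measures on a caregiver. Report it beside the paired test.
3. Name child age among the covariates in Outcomes and Measures: Caregiver Cohort.
4. Report the dose analysis as supporting evidence, noting that listeners are self-selected.
5. State that Table 3's 80% power refers to the paired change, not the age-adjusted one.

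The difference-in-differences model needs no change.

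The cost is wording plus one model on birth dates and interview dates already collected, although some ages are approximate. The downsides should be stated. The adjusted standard error is about 1.6–1.7 times larger, so power for 5 points is about 38–42%. Only about half of each survey overlaps in age, so the time effect comes mainly from children aged 12–23 months and assumes the same radio effect at other ages. Age adjustment does not remove secular trend, repeat-interview effects, or the effect of the thank-you toy offered at baseline on a toy-in-home indicator. The adjusted result therefore still does not establish radio against no radio.
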